## Protocol Questionnaire

**Human Subject Research**

Does the protocol meet the federal definition of research? For help determining the type of research you are conducting, see the DHHR Human Subject Regulations Decision Charts at <http://www.hhs.gov/ohrp/policy/checklists/decisioncharts.html>.

Yes

Does the research involve living person(s)?

Yes

Will information from individual person(s) be collected as part of this research?

Yes

**Funding Source**

Is there a secured funding source?

No

**Locations of Research**

Select the location(s) where the research will be conducted. At least one location must be selected.

Physicians Office Center (POC)

Select the location(s) where the research will be conducted. At least one location must be selected.

WVU Campus

Select the location(s) where the research will be conducted. At least one location must be selected.

Ruby Memorial Hospital or Other WVU Healthcare Site

Will the research take place at an off campus location?

No

Will this study require an Inter-Institutional Authorization Agreement (IAA)?

No

**Design**

Please provide a lay summary (written at 6th grade level) that includes a statement about the purpose and the general aims of the research.

This study is designed to examine if immediate weight bearing on a distal femur fracture fixed with a primary locking plate, either a distal condylar locking plate or a LISS (less invasive stabilization system), is safe and promotes more rapid fracture healing. Historically and currently patients are kept partial weight bearing after fixation of these fractures for 6-12 weeks until callous formation is observed on radiographs. Our hypothesis is that patients that are allowed to bear weight immediately will heal at least as quickly as those that have their weight bearing status protected with the added benefits from early mobilization. Fracture healing will be monitored closely by follow up appointments and complications will be documented.

Fully describe all procedures to be performed, from start to finish, numbering your procedures 1,2,3 or A, B, C (e.g., 1. Recruiting, 2. Consent, 3. Collecting data, 4. How findings will be shared, etc.).

1. Patients will come to the Emergency Department or the POC after a supracondylar fracture or periprosthetic distal femur fracture. 2. If they fit all the inclusion and none of the exclusion criteria they will be told about the study either before their surgery if they are lucid, not in pain and can understand the study, or after their surgery when they are lucid, not in pain and can understand the study. If they are not lucid, are in pain, or cannot understand the study during this time they will not be offered participation in the study. 3. They will be told about the study with the understanding that assignment to either partial weight bearing or full weight bearing is standard of care and that physical therapy will conduct the therapy based on their group assignment 4. All questions will be answered and the subject will be given the opportunity to consent 5. They will have a metabolic bone work up done if they are 65 years of age or older which is standard of care. 6. Radiographs will be taken at 6 weeks, 3, 6 and 12 months to determine radiographic healing and/or complications with hardware which is standard of care. 7. Two independent surgeons will review radiographs to determine bridging of 3 or 4 cortices 8. We will measure time to ambulation at 2 weeks, 6 weeks and 3 months. Other variables measured include: Age, gender, date of surgery, Surgeon, Rt/Left, plate (LISS or Locking), smoking status, co-morbidities, perambulatory status, PT participation, time to discharge, discharge disposition, return to baseline ambulation, time to union, pain, Knee society score, knee flexion, radiographic evidence of healing, non-union, malunion, infection, DVT, PE, implant failure/reoperation, Vit D level, death. 9. Patients will complete a health progress report at 2 weeks, 3, 6, and 12 months post-surgery which is standard of care.

Please describe the investigational procedures that will be performed throughout the duration of the study.

Reviewing who heals faster with better outcomes based on assignment to full or partial weightbearing, both of which are standard of care, but for the study, the subject is assigned to one or the other.

Please describe the standard of care procedures that will be performed throughout the duration of the study.

Surgery and anything associated with it.

Will you be assigning or randomizing participants to groups or conditions (e.g., control, placebo)?

Yes

Describe the group assignment.

We will be looking at two groups: those with periprosthetic distal femur fracture and those with a distal femur fracture proximal to the native knee. Both will have had their distal femur fracture repaired per standard of care. Patients in both groups will then be randomized into two groups: those allowed to bear weight immediately post operatively and those with protected weight bearing post operatively.

Does the research involve surveys/interviews/questionnaires? If so, attach a copy of the interview/survey questions on the Notes & Attachments page.

No

Describe what is known about this topic and why this study is needed. Please include at least two reference citations to support your rationale.

This study is designed to examine if immediate weight bearing on a distal femur fracture fixed with a primary locking plate, either a distal condylar locking plate or a LISS (less invasive stabilization system), is safe and promotes more rapid fracture healing. Historically and currently patients are kept partial weight bearing after fixation of these fractures for 6-12 weeks until callous formation is observed on radiographs. Our hypothesis is that patients that are allowed to bear weight immediately will heal at least as quickly as those that have their weight bearing status protected with the added benefits from early mobilization. Fracture healing will be monitored closely by follow up appointments and complications will be documented. See Lit Review under Notes and Attachments for Scientific Rationale and references.

What method are you going to use to analyze the data?

Descriptive statistics will be performed on the following variables in both groups: Age, gender, date of surgery, Surgeon, Rt/Left, plate (LISS or Locking), smoking status, co-morbidities, perambulatory status, PT participation, time to discharge, discharge disposition, return to baseline ambulation, time to union, pain, Knee society

score, knee flexion, radiographic evidence of healing, non-union, malunion, infection, DVT, PE, implant failure/reoperation, Vit D level, death.

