### Subjects

Indicate the maximum number of subjects to be enrolled or medical records to be reviewed at all sites by the WVU or VAMC research team.

150

Provide a rationale for choosing your sample size.

75 in each group provides 80% power to detect a difference between the groups.

State the requirement(s) to become a participant in the study (e.g., age range, sex, language spoken, class enrollment/ranking).

All patients aged > 18 yo with a distal supracondylar femur fracture will be included, both male and female; Supracondylar distal femur fractures treated with a locked plate, either a distal condylar locking plate or a LISS (less invasive stabilization system), including peri-prosthetic fractures. CPT code 27511

Explain why selection of participants will be equitable addressing gender, ethnicity, and/or race of subjects.

Patients with an intracondylar split, polytrauma patients with associated trauma that will inhibit their ability to weight bear, metastatic disease, incomplete follow up, those with questionable ability to bear weight (ie advanced dementia), open fractures with bone loss, will not be included. Those who are in pain, not lucid, or unable to understand the study at time of consent will not be included.

In outline format and chronological order, describe what will be done to identify and recruit participants (e.g., A, B, C or 1, 2, 3).

1. Patients will come to the Emergency Department or the POC after a supracondylar fracture or periprosthetic distal femur fracture. 2. If they fit all the inclusion and none of the exclusion criteria they will be told about the study either before their surgery if they are lucid, not in pain and can understand the study, or after their surgery when they are lucid, not in pain and can understand the study. If they are not lucid, are in pain, or cannot understand the study during this time they will not be offered participation in the study.

Will any of the subjects be less than 18 years old?

No

Will your study target populations such as pregnant women, fetuses, neonates, or any groups likely to be vulnerable to coercion or undue influence such as children, prisoners, individuals with impaired decision-making capability or economically or educationally disadvantaged persons?

No

Does this research involve participants who could be coerced or unduly influenced, such as current students/employees of research team members?

No

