### **Potential Benefits**

Is there any known benefit to the individual subject as a result of participating in the research? Payments to subjects should not be included in this section, but addressed in the Payments/Reimbursements section.

If our hypothesis is correct, those subjects who do full weight bearing will heal faster and suffer less complications.

Describe the potential benefit(s) to society and/or scientific / medical knowledge of the planned work.

Understanding and sharing information gathered from the research study re: benefit or no benefit to full weight bearing after a supracondylar distal femur fracture.

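### The protocol asks whether immediate weight bearing is safe, but plans no between-arm comparison, interval or criterion for complications that could answer it

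*Combined protocol and SAP*

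**What the plan says.** The lay summary in the Design section, repeated in the rationale answer there, asks whether immediate weight bearing "is safe and promotes more rapid fracture healing". The hypothesis named in both places concerns healing: patients allowed to bear weight at once "will heal at least as quickly as those that have their weight bearing status protected". The Potential Benefits section adds that, if the hypothesis is right, "those subjects who do full weight bearing will heal faster and suffer less complications".

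The procedures in the Design section list the complications singly among the other variables: "non-union, malunion, infection, DVT, PE, implant failure/reoperation, Vit D level, death". The lay summary says that complications will be recorded. The answer on analysis method, also under Design, reads "Descriptive statistics will be performed on the following variables in both groups", followed by the same list, in which complications stand beside age, surgeon and plate type.

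The Subjects section gives the whole sample size rationale in one sentence: "75 in each group provides 80% power to detect a difference between the groups". It names no outcome, event rate, effect size or significance level.

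**The concern.** Safety is a stated question of the study, and answering it means saying how large an excess of complications the data rule out. That takes a chosen outcome, a comparison between the randomised arms, an interval for that comparison, and a limit against which to read it. The plan has none of these. Two columns of counts do not supply them, and the reader is left to judge by eye whether the columns look alike.

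The Design section says that patients are historically and currently kept partial weight bearing for 6 to 12 weeks, so a conclusion of safety would bear directly on that practice. If complications are uncommon, 75 per arm can show no significant difference while the data remain compatible with a substantial relative excess. The plan neither tells the authors to report that uncertainty nor says what result would count as inconclusive.

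**Working it through.** **Inputs.** From the Subjects section: 75 per group, 150 at most, 80% power. I read the groups as the two weight-bearing arms. That is the natural reading, although the group-assignment answer under Design also calls the two fracture types groups before saying "Patients in both groups will then be randomized into two groups". The documents give no complication rate, significance level or dropout allowance. Assumed here: two-sided 5%, no loss, and complication rates of 5%, 10%, 15% and 20%.

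**The plan's own figure.** The 80% power cannot be reproduced, because outcome, effect and significance level are missing. Solving backwards for a binary outcome, 75 per arm gives 80% power for 5% against 20.1%, 10% against 27.8%, or 15% against 34.7% (two-sided 5%, no continuity correction).

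**Step 1: interval for the risk difference when both arms show the same rate p.** Half-width = 1.96 × √(2p(1−p)/75).
- 5%: 1.96 × √(0.095/75) = 1.96 × 0.0356 = 7.0 points
- 10%: 1.96 × √(0.18/75) = 1.96 × 0.0490 = 9.6 points
- 15%: 1.96 × √(0.255/75) = 1.96 × 0.0583 = 11.4 points
- 20%: 1.96 × √(0.32/75) = 1.96 × 0.0653 = 12.8 points

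A doubling adds p. It lies outside the interval when the half-width is below p, that is when 0.1024 × (1−p) < p, or p > 0.1024/1.1024 = 9.3%. On this scale, equal observed rates fail to exclude a doubling only below about 10%.

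**Step 2: the same on the risk-ratio scale.** Upper 95% limit = exp(1.96 × √(2(1−p)/(75p))).
- 5%: exp(1.96 × 0.712) = 4.04
- 10%: exp(1.96 × 0.490) = 2.61
- 15%: exp(1.96 × 0.389) = 2.14
- 20%: exp(1.96 × 0.327) = 1.90

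The limit falls below 2 once p reaches about 17.6%. On this scale a doubling is not excluded below about 18%.

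**Step 3: power to detect a true doubling** (two-sided 5% two-proportion z test, pooled variance under the null). For 10% against 20%: (0.10 − 1.96 × 0.0583)/0.0577 = −0.25, which gives 40%. By the same formula:

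| Comparison | 75 per arm | 60 per arm (assumed 20% loss) |
|---|---|---|
| 5% v 10% | 21% | 18% |
| 10% v 20% | 40% | 33% |
| 15% v 30% | 60% | 50% |
| 20% v 40% | 77% | 67% |

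Power reaches 80% at 75 per arm only from a control rate of about 21%.

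**Step 4: chance of excluding a doubling when the true rates are equal.** On the ratio scale, by exact summation over the possible counts, it is 14% at 5%, 29% at 10%, 42% at 15% and 56% at 20%. On the risk-difference scale at 10%, the normal approximation gives 0.10/0.0490 − 1.96 = 0.08, or about 53%.

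**Step 5: the expectation of fewer complications.** With 75 per arm, power to detect a halving is 12% from 5%, 21% from 10% and 40% from 20%. About 80% power needs a fall as large as 20% to 5%.

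**Step 6: no events.** Zero events in 75 leaves an upper limit of 1 − 0.05^(1/75) = 3.9% (one-sided 95%) or 1 − 0.025^(1/75) = 4.8% (two-sided 95%).

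**The case against.** The strongest reply is that the size of the problem depends on an unknown rate and on the scale chosen. This is correct. A reader might infer that 75 per arm can never exclude a doubling of failures. Steps 1 and 2 do not support that: with equal observed rates, a doubling is excluded on the risk-difference scale from about 10% and on the risk-ratio scale from about 18%. A composite of the listed complications might reach such rates.

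A reader might also infer that similar counts are to be expected even if harm doubles. They are not. With 75 per arm, exact binomial calculation puts the chance that the two counts fall within two of each other at 33% for 5% against 10%, 11% for 10% against 20%, and 4% for 15% against 30%. A non-significant result is not the same as similar counts, and at 15% a significant result is more likely than not.

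Nor do the documents say that an absence of difference will be taken as proof of safety. They set no rule for a null result, so the fair statement is that nothing in the plan prevents that reading. The sentence on fewer complications is a conditional answer to a form question about benefit to the subject, not the named hypothesis, and should not be treated as a formal superiority objective. The literature review attached to the submission is not available here and may give rates.

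What survives is the absence of a method. The question on analysis was asked directly and answered with descriptive statistics alone, and safety is put as a question in both the lay summary and the rationale.

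**Conclusion.** The concern holds in a conditional form. Safety is asked about, and the planned analysis cannot say how much excess harm is excluded, whatever the true rate, because no comparison, interval or criterion is specified. The numerical size is an illustration under assumed rates, 75 evaluable per arm and a two-sided 5% level. Risk differences would be known to within about 7 to 13 points for rates of 5% to 20%, and power to detect a doubling is 60% or less for control rates up to 15%. Equal observed rates leave a doubling open below about 10% on the difference scale and below about 18% on the ratio scale. Any loss to follow-up makes these figures worse, and the Subjects section makes no allowance for it. The change should be made: it costs little and affects what the study may conclude.

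**What to change.** In the analysis answer under Design:

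1. Name one mechanical-failure outcome from the variables already collected, for example implant failure/reoperation or non-union, as the main safety outcome, with its definition and time point.
2. Report the risk difference by assigned arm with its 95% interval for that outcome and for each other complication. Where counts are small, a Newcombe interval is preferable to the simple one in Step 1. With 4 of 75 in each arm, for instance, it gives ±8.3 points.
3. Conclude that immediate weight bearing is safe only if the upper limit lies below a margin that the investigators set in advance; otherwise report the result as inconclusive.
4. State the assumed complication rate and the interval width it implies, so that readers know beforehand what the study can exclude.

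In Potential Benefits, do not present fewer complications as something the trial is sized to show.

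The cost is some wording, one interval per complication, and a safety claim that may come out less favourable. No extra patients, visits or data are required.

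### Union is known only to lie between two scheduled films, so a mean or median of first-bridged film dates is not a healing time and can hide or exaggerate a difference between arms

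*Combined protocol and SAP*

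**What the plan says.** The lay summary under Design asks whether immediate weight bearing "is safe and promotes more rapid fracture healing", and states the hypothesis that "patients that are allowed to bear weight immediately will heal at least as quickly as those that have their weight bearing status protected". No margin is attached to it.

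Healing is observed on films. Item 6 of the procedures says: "Radiographs will be taken at 6 weeks, 3, 6 and 12 months to determine radiographic healing and/or complications with hardware which is standard of care". Item 7 adds: "Two independent surgeons will review radiographs to determine bridging of 3 or 4 cortices". The variables in item 8 include "return to baseline ambulation, time to union, pain, Knee society score, knee flexion, radiographic evidence of healing, non-union".

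The answer on method of analysis, also under Design, reads "Descriptive statistics will be performed on the following variables in both groups", and the list that follows contains "return to baseline ambulation, time to union, pain, Knee society". The documents do not say:
- how union is dated between films;
- whether nominal or actual film dates are used;
- how a patient not bridged at the last film is counted;
- whether an unscheduled film would count.

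**The concern.** A fracture first seen as bridged on the 6-month film united at some point after the 3-month film. The film date is the upper end of that interval. If it is entered as the time to union and then averaged, the summary reflects the visit calendar as well as the biology.

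Healing speed is the central question, so this matters. Two arms with medians inside the same interval give the same recorded median however far apart they are within it. Two arms with medians just either side of a film give recorded medians a whole interval apart. Because the hypothesis is of the no-worse kind and has no margin, a reader could take equal recorded medians as confirming it when they show only that both medians fell between the same two films.

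**Working it through.** **Plan's own figure.** The documents give no precision, distribution or expected value for time to union, so there is nothing to reproduce. They refer to an attached literature review that is not part of the text reviewed. The healing times below are therefore assumptions.

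**Intervals.** Taking 3, 6 and 12 months as 13, 26 and 52 weeks, the gaps are 6 − 0 = 6, 13 − 6 = 7, 26 − 13 = 13 and 52 − 26 = 26 weeks.

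**Model.** True union times are lognormal with median *m* and log-SD σ = 0.45 (0.30 as a check). The share bridged by a film at week *t* is Φ(ln(*t*/*m*)/σ). The recorded time is the first film at or after true union, with anything beyond 52 weeks set to 52.

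**A delay within one interval: 16 v 22 weeks**
- 3 months, *m* = 16: Φ(ln(13/16)/0.45) = Φ(−0.461) = 32%. *m* = 22: Φ(ln(13/22)/0.45) = Φ(−1.169) = 12%.
- 6 months, *m* = 16: Φ(ln(26/16)/0.45) = Φ(1.079) = 86%. *m* = 22: Φ(ln(26/22)/0.45) = Φ(0.371) = 64.5%.
- Both arms pass 50% between the 3- and 6-month films, so both recorded medians are 26 weeks and the difference is 0 against a true 6. True medians of 14 v 24 weeks also both give 26.
- With σ = 0.30 the recorded medians are again both 26; the shares are 24% v 4% at 3 months and 95% v 71% at 6 months.

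**A small delay that crosses a film**
- 12.5 v 13.5 weeks: the shares bridged at 13 weeks are Φ(0.087) = 53.5% and Φ(−0.084) = 46.7%. The recorded medians are 13 and 26, so a 1-week difference becomes 13.
- 24 v 28 weeks: the shares at 26 weeks are Φ(0.178) = 57% and Φ(−0.165) = 43%. The recorded medians are 26 and 52, so a 4-week difference becomes 26.

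In a large sample the recorded median is the first film at or after the true median, whatever the spread. The median results therefore depend on where the true medians lie, not on the lognormal shape.

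**Means: 16 v 22 weeks, σ = 0.45**
- True means are *m*·exp(σ²/2): 17.7 and 24.3, a difference of 6.6.
- Recorded, *m* = 16: 6(0.0146) + 13(0.3076) + 26(0.5374) + 52(0.1403) = 25.4.
- Recorded, *m* = 22: 6(0.0019) + 13(0.1192) + 26(0.5236) + 52(0.3553) = 33.7.
- The recorded difference is 8.3. The means are inflated by about 8 and 9 weeks, and the difference between arms is overstated.

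**What the same films retain.** For 16 v 22 weeks the proportions differ by 20 points at 3 months and 21 at 6 months, where the recorded medians differ by 0.

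**Power, 75 per arm, two-sided 0.05, same model.** By simulation, a rank test on the recorded visit times has about 97%, a t-test on exact times about 98.5%, and a comparison of the 3-month proportion alone about 86%.

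**The case against.** The strongest reply is that the schedule is the same in both arms, so it favours neither, and that little information is lost for detecting a difference. Both statements are correct. In the example a rank test on visit categories keeps nearly all the power of exact times. The plan also lists radiographic evidence of healing as a variable separate from time to union, and a simple frequency table by visit would show the proportions. Nor does the plan single out the median; a mean would have shown the 16 v 22 week delay, somewhat enlarged. What this reply leaves untouched is that descriptive statistics of time to union, with no dating rule, allow visit dates to be reported as weeks of healing.

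Several stronger readings are tempting, but the documents do not support them:
- *The schedule biases the result towards healing at least as quickly.* It does not: a delay across a film is magnified, and the recorded mean difference above exceeds the true one.
- *The hidden delay is at most about 13 weeks.* That is the 3-to-6-month gap. The 6-to-12-month gap allows just under 26.
- *Time to union can take only four values.* This assumes nominal visit times, which the plan does not specify. Actual film dates would give more values with the same interval uncertainty, and non-union is listed separately. The plan says "Fracture healing will be monitored closely by follow up appointments and complications will be documented", and it does not exclude unscheduled films, though it plans none.
- *The outcome is too coarse even for a proper test.* The power figures contradict this.

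**Conclusion.** The point holds as one of lost resolution and distortion without a fixed direction. On the planned schedule, union is located only to within 6 to 26 weeks, and the only stated analysis would allow the upper end of that interval to be summarised as a healing time. In the worked cases, a true difference of 6 weeks in medians is recorded as 0 and one of 1 week as 13; means are inflated by about 8 to 9 weeks.

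The percentages, means and power figures rest on assumed lognormal times. The interval widths follow from the schedule alone. The 12.5 v 13.5 week case is a large-sample result: with 75 per arm and shares so close to 50%, either sample median could fall on either side of the film.

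The practical risk is of interpretation: without a margin, equal recorded medians could be taken as evidence for the hypothesis. The data to avoid this are already being collected, so the matter is worth correcting but not fatal.

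**What to change.** Amend the analysis answer under Design as follows.

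1. Analyse time to union by assigned arm as interval-censored between the last unbridged and first bridged film, using actual film dates. Right-censor patients not bridged at their last film.
2. Report the proportion bridged by assigned arm at each scheduled film (6 weeks, 3, 6 and 12 months), with the difference and its confidence interval.
3. Give no mean or median of visit dates as weeks to union.
4. Because it sets the ends of each interval, state what counts as bridged (3 or 4 cortices), how disagreement between the two readers is settled, and whether unscheduled films count.

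The 3-month proportion should not be the sole main comparison: in the example it has about 86% power, against about 97% for a rank test on all the visit categories.

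The change is to wording and analysis only; the films, readers and patients stay the same. The costs are slightly more analysis work and the loss of a simple average number of weeks.

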### Expedited Review

Is this study only minimal risk?

Yes

Does the research qualify for Expedited Review Category 1 - clinical studies of FDA-approved drugs or medical devices? (See More Information)

No

Does the research qualify for Expedited Review Category 2 - blood sample collection? (See More Information)

No

Does the research qualify for Expedited Review Category 3 - noninvasive collection of biological specimens? (See More Information)

No

Does the research qualify for Expedited Review Category 4 - noninvasive standard of care procedures? (See More Information)

No

Does the research qualify for Expedited Review Category 5 - evaluation of data (e.g., medical records review)? (See More Information)

Yes

Does the research qualify for Expedited Review Category 6 - voice, video, digital, or image recordings? (See More Information)

No

Does the research qualify for Expedited Review Category 7 - behavior, surveys, interviews, etc.? (See More Information)

No

Briefly describe how the research meets the requirements of the expedited category(ies) selected.

Full or partial weight bearing after a supracondylar distal femur fracture is standard of care. Review of medical records to determine the variables we want to collect: standard of care patient reported outcomes at regular follow up visits.

Does the study involve intervention and/or manipulation of the subjects or the subjects' environment (e.g., educational intervention or training, experimental or quasi-experimental design)?

No

Is the research categorized as interventional medical research?

No

Will subjects intentionally be deceived as to the purpose of the study?

No

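### The two-surgeon film review is specified for cortical bridging only; no independent or masked reading is specified for hardware failure or malunion, although safety is a stated aim

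*Combined protocol and SAP*

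**What the plan says.** All of this is in the combined protocol and SAP.

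- **Aim.** The lay summary in the Design section asks whether immediate weight bearing "is safe and promotes more rapid fracture healing". It adds that complications will be recorded, but names no person or process.
- **Films.** Procedures, item 6: "Radiographs will be taken at 6 weeks, 3, 6 and 12 months to determine radiographic healing and/or complications with hardware".
- **Independent reading.** Procedures, item 7: "Two independent surgeons will review radiographs to determine bridging of 3 or 4 cortices". The surgeons are given no other reading task. The item does not say what they are independent of, or whether they are masked to allocation.
- **Outcomes collected.** The item 8 list ends with "radiographic evidence of healing, non-union, malunion, infection, DVT, PE, implant failure/reoperation, Vit D level, death". Malunion and implant failure/reoperation have no stated definition, reader or adjudication.
- **Data source.** Expedited Review section: "Review of medical records to determine the variables we want to collect: standard of care patient reported outcomes at regular follow up visits".
- **Who delivers the allocation.** Procedures, item 3: "physical therapy will conduct the therapy based on their group assignment".
- **Expectation.** The Potential Benefits section says that, if the hypothesis is right, full weight bearing brings faster healing and fewer complications.
- **Analysis.** The Design section plans descriptive statistics in both groups and no other method.

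**The concern.** The films are taken to answer two questions, but an independent reading is arranged for only one of them. Healing gets two readers. Plate or screw failure and malunion, which can show on the same films and bear directly on safety, get no specified reader.

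Screw loosening and malalignment are judgements. Whether they are noted depends partly on who looks, how carefully, and what that person expects. Weight bearing cannot be hidden from patients or therapists, and treating clinicians will ordinarily know it. The team has written down an expectation that favours one arm. Because the analysis is descriptive, the recorded rates are themselves the safety result, and no later step would correct unequal detection. The trial could report a reassuring comparison that reflects recording habits, or an alarming one for the same reason.

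**Working it through.** **Step 1. Set the passages side by side.**

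| Outcome | Shown on scheduled films? | Reader stated? | Definition stated? | Masking stated? |
|---|---|---|---|---|
| Bridging | Yes (item 6) | Two independent surgeons (item 7) | 3 or 4 cortices | No |
| Hardware failure | Yes in part (item 6); listed jointly with reoperation (item 8) | No | No | No |
| Malunion | Yes, by its nature | No | No | No |

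The asymmetry in reader and definition is in the text. Masking is absent for all three.

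**Step 2. What unequal recording would do.** The documents give no complication rates or capture rates, so there is no figure of the plan's own to reproduce. The sample-size statement (75 per group, 80% power) names no endpoint and does not bear on this point. All rates below are assumptions.

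Let p0 and p1 be the true rates in the protected and immediate arms, and s0 and s1 the proportions of true events recorded.

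- Observed rate = p × s
- Observed difference = p1·s1 − p0·s0
- Observed ratio = (p1/p0) × (s1/s0)

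Take p0 = 10% and p1 = 15%. The true difference is 5 points and the true ratio 1.5.

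| s0 | s1 | Observed, protected | Observed, immediate | Difference | Ratio |
|---|---|---|---|---|---|
| 90% | 60% | 0.10 × 0.90 = 9.0% | 0.15 × 0.60 = 9.0% | 0 | 1.0 |
| 90% | 70% | 9.0% | 0.15 × 0.70 = 10.5% | 1.5 points | 1.17 |
| 70% | 70% | 0.10 × 0.70 = 7.0% | 10.5% | 3.5 points | 1.5 |
| 60% | 90% | 0.10 × 0.60 = 6.0% | 0.15 × 0.90 = 13.5% | 7.5 points | 2.25 |

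The harm disappears when s1/s0 = p0/p1 = 0.10/0.15 = 0.67. The reverse imbalance exaggerates it. Equal under-recording shrinks the difference but leaves the ratio unchanged.

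**Step 3. No true difference.** With 20% in both arms, capture of 90% (protected) and 70% (immediate) gives 18% against 14%, a spurious 4-point advantage for immediate weight bearing. Swapping the capture rates gives a spurious 4-point harm.

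**Step 4. Scale in patients.** With 75 per group, a 5-point difference is 0.05 × 75 = 3.75 patients. In the 90%/60% row the missed events are 0.10 × 75 × 0.10 = 0.75 (protected) and 0.15 × 75 × 0.40 = 4.5 (immediate). A few unrecorded findings in one arm are enough to remove the difference.

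**The case against.** The strongest reply is that this reads silence as exclusion. Item 7 sits directly after item 6 and may simply state the bridging criterion. It does not say that the surgeons ignore the hardware. Item 8 says the team will measure the listed variables. The Confidentiality section says a coded spreadsheet already exists, and it may have such fields; it is not in the documents. This stands as a caution, but a plan that arranges a two-reader assessment for one film outcome should say who reads the others.

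A reader might infer more than the documents support:

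- **That the clinicians who apply the assigned weight bearing also record the complications.** The only group said to apply it is physical therapy, and nothing says that therapists read films or record complications. That treating clinicians know the arm is a reasonable inference, not a documented fact.
- **That chart sourcing is established.** The Expedited Review sentence goes on to patient-reported outcomes, and it cannot be exhaustive because bridging comes from the surgeons' reading. Records as the source for hardware failure and malunion are an inference.
- **That the bridging review is already protected from bias.** Masking is not stated there, so handing the surgeons more to read would not by itself remove arm-dependent detection.
- **That the bias favours a conclusion of safety.** The capture rates are assumed, and the reversed pair exaggerates harm.

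Two further objections stand and shape the fix. A failure found and revised between scheduled films may appear on none of them, so film reads cannot simply replace the clinic note. And implant failure is listed together with reoperation, so it is only partly a film outcome.

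It can also be said that, with descriptive analysis only, the choice of reader is a refinement. That limits the weight of the point, but descriptive rates have no other safeguard.

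**Conclusion.** The point holds in limited form. The plan specifies an independent two-surgeon reading for bridging and specifies no independent or masked reading for hardware failure or malunion, although the same films are taken partly to detect hardware complications and safety is a stated aim. That much rests on the text.

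The size of any bias is unknown, and so is its direction. Under the assumed 10% and 15%, a true 5-point difference could be observed as anything from 0 to 7.5 points across the capture pairs shown. This depends on assumed rates and on recording that differs by arm, which the documents neither establish nor guard against. They do not support saying that the safety result will be biased towards no harm, or that the people applying the intervention are recording its complications.

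This is not a contradiction in the plan. It is a gap in the evidence for a stated aim that readers and films already planned can close cheaply, so it should be changed.

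**What to change.** Extend item 7 of the procedures as follows.

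1. At the same reading, the same two surgeons also record for each film, yes or no: plate or screw breakage, screw loosening or pull-out, and malalignment against a prespecified definition.
2. The films are supplied without the allocation. Where possible, neither surgeon reads films of their own patients. The same conditions apply to the bridging reads.
3. State the rule for disagreement between the two readers.
4. Derive non-union from the bridging reads at a stated time point.
5. Use these reads as the main source for radiographic complications by arm.
6. Keep from the chart all reoperations and any documented failure found between scheduled films. Implant failure/reoperation then counts an event from either source and is also reported by source, so that differences in recording between arms can be seen.

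The cost is a few extra columns on the reading sheet, a little more reading time per film, and the writing of the definitions and rules. No extra films, readers or visits are needed, and the sample size is unaffected.
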